2.4.4 Analyses of efficacy endpoints

For statistics where international and conventional units do not impact the results (eg, means and least square (LS) means for percent changes from baseline, rates of patients below a threshold), derivations will be done and statistical models will be run using conventional units. For other statistics (eg, descriptive statistics at baseline and over time, absolute changes from baseline), derivations will be done with both international and conventional units.

There will be no formal statistical test for the efficacy endpoints. All efficacy analyses will be descriptive.

2.4.4.1 Analysis of primary efficacy endpoint(s)

The analysis will be based on an on-treatment approach, and will use LDL-C values collected during the OLDFI efficacy treatment period. The OLDFI efficacy treatment period is defined as the period from first OLDFI IMP injection to last OLDFI IMP injection +21 days (for Cohorts 1 & 2) or + 35 days (for Cohorts 3 & 4) . For patients entering in the OLE, the OLDFI efficacy treatment period will be truncated at the day before the first OLE IMP injection in the extension period.

The percent change from baseline in calculated LDL-C at Week 8 as defined in [Section 2.1.3.1](#) will be analyzed in the mITT population using a mixed-effect model with repeated measures (MMRM) approach to handle missing data. All post-baseline data available during the OLDFI efficacy treatment period (Week 4 and Week 8) and within analysis windows will be used and the missing data will not be imputed. The model will include the fixed categorical effects of alirocumab doses/dose regimen (30 mg Q2W [<50 kg], 40 mg Q2W [<50 kg], 50 mg Q2W [≥ 50 kg], 75 mg Q2W [≥ 50 kg], 75 mg Q4W [<50 kg], 150 mg Q4W [≥ 50 kg], 150 mg Q4W [<50 kg] and 300 mg Q4W [≥ 50 kg]), time point (Week 4, Week 8 as defined in [Section 2.5.4](#)), dose-by-time point interaction, as well as, the continuous fixed covariates of baseline LDL-C value and baseline value-by-time point interaction.

This model will be run using SAS Mixed procedure with an unstructured correlation matrix to model the within-patient errors. Parameters will be estimated using restricted maximum likelihood method with the Newton-Raphson algorithm. Denominator degrees of freedom will be estimated using Satterthwaite's approximation. This model will provide baseline adjusted least-squares means estimates at Week 8 for each alirocumab dose, with their corresponding standard errors (SEs) and 95% confidence intervals (CIs). In addition, LS mean with 95% confidence intervals will be provided for each cohort using appropriate contrasts.

Additionally, for Cohort 4 only, the percent change from baseline in calculated LDL-C at Week 12 will be analyzed using the same model as for the primary endpoint: All post-baseline data available during the open-label dose-finding treatment period and within analysis windows for Cohort 4 will be used and the missing data will not be imputed. The model will include the fixed categorical effects of alirocumab doses/dose regimen (150 mg Q4W [<50 kg] and 300 mg Q4W [≥ 50 kg]), time point (Week 4, Week 8, Week10, Week 12), dose-by-time point interaction, as well as, the continuous fixed covariates of baseline LDL-C value and baseline value-by-time point. This model will provide baseline adjusted least-squares means estimates at Week 12 for each alirocumab dose of Cohort 4, with their corresponding SEs and 95% CIs. In addition, LS mean with 95% confidence intervals will be provided for Cohort 4 overall using appropriate contrasts.

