- p Pregnancy test with a local urine pregnancy test should be done on females of childbearing potential who are sexually active or females who have experienced menarche.
- q See [Appendix E](#) for Tanner stages evaluation.
- r Diary completion starts from Pre-filled Syringe dispensation.

1.4.2 COHORT 4

Extension Phase Cohort 4		Open-Label Extension (OLE) Period				
Week (W)		W12	W16, W20^o	W24	W36	W48 (EOS/End of OLE^b)
Visit Number		8^a	9, 10	11	12	13 (or Visit 20 for eCRF)
Visit Window (+/- days)			±7	±14	±14	±7
Eligibility requirement^c		X				
Physical Examination					X	X
Body Weight		X			X	X
Height		X			X	X
Tanner Stages^m		X			X	X
IVRS/IWRS contact		X		X	X	X
Treatment:						
Alirocumab Injection – PREFILLED SYRINGE ^d		X	X	X	X	
Concomitant Medication		X	X	X	X	X
Review of diet		X	X	X	X	X
Compliance check of alirocumab injections (prefilled syringe – if applicable)			X	X	X	
Diary ⁿ		X	X ^o	X	X	
Check of stability of background LMT		X	X	X	X	
Efficacy:						
Total-C, calculated LDL-C, HDL-C, TG, non-HDL-C ^e		X		X	X	

Extension Phase Cohort 4		Open-Label Extension (OLE) Period					
Week (W)		W12	W16, W20 ^o	W24	W36	W48 (EOS/End of OLE ^b)	Follow-up Phone contact at least 10 weeks after last IMP
Visit Number		8 ^a	9, 10	11	12	13 (or Visit 20 for eCRF)	14
Visit Window (+/- days)			±7	±14	±14	±7	±7
Safety:							
AE /SAE recording (if any)		X	X	X	X	X	X
Vital Signs		X			X	X	
Laboratory Testing^e:							
Hematology and chemistry ^f				X		X	
Creatine phosphokinase (CPK)				X		X	
Liver panel ^g				X		X	
Anti-alirocumab antibodies (ADA) ^h		X		X		X	
Adrenal gland hormones ⁱ				X		X ^h	
Gonadal and pituitary hormones ^j				X		X	
Fat soluble vitamins ^k				X		X	
Pregnancy test ^l		X		X	X	X	

a The first visit of the OLE period from the extension phase will overlap with the final visit of the 12-week dose-finding treatment period.

b The end of open-label extension period visit will take place at least 4 weeks after the last alirocumab administration (with a follow-up phone call at least 10 weeks after the last alirocumab administration) before the initiation of the pediatric Phase 3 study in the site where the patient is potentially participating or December 2018 at the latest.

c In order to enter into the extension phase, the patient must successfully complete the 12-week open-label dose-finding treatment period.

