During the open-label extension period for Cohort 3, the first injection administration will start at Week14 after the last injection administration at Week 4 (ie, 10 weeks after the last administration of alirocumab). The treatment kit number will be provided by IRT according to the last dose administered in Cohort 3. The first injection of the extension period will be done at the site by the investigator staff. If the self-injections by patient or another designated person (such as parent, nurse, etc.) are decided during the extension period a training injection should be planned 4 weeks before the first self-injection, under direct site staff supervision.

During the open-label extension period for Cohort 4, the first injection administration will start at Week 12 at the end of the 12-week open-label dose finding. The treatment kit number will be provided by IRT according to the last dose administered in Cohort 4. The first injection of the extension period will be done at the site by the investigator staff. If the self-injections by patient or another designated person (such as parent, nurse, etc.) are decided during the extension period a

training injection should be planned 4 weeks before the first self-injection, under direct site staff supervision.

During the extension treatment period, IMP should ideally be administered every 2 weeks SC or every 4 weeks at approximately the same time of the day; however it is acceptable to have a window period of ± 3 days. The time of the day is based on visit's time or patient's preference in case of self-injections.

If by mistake or due to other circumstances an injection is delayed by more than 7 days or completely missed (for Cohorts 1 and 2) or by more than 14 days or completely missed (for Cohort 3 and Cohort 4), then the patient should return to the original schedule of study treatment administration without administering delayed injections. On the other hand, if the delay is less than or equal to 7 days (for Cohorts 1 and 2) from the missed date or if the delay is less than or equal to 14 days for (Cohort 3 and Cohort 4) from the missed date, then the patient should administer the delayed injection and then resume the original schedule of study treatment administration.

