10.1.4 Open label extension treatment period (OLETP, optional)

Patients who successfully complete the main treatment period and follow-up period will be eligible (provided they have not experienced AEs leading to permanent discontinuation during the main treatment period, or had significant protocol deviations, in the Investigator's judgment) to enter an optional open-label treatment period. Treatment for these patients will start after the follow-up period and the last dose/dose regimen of the main treatment period should be administered again during this extension period (start Week 16 for Cohorts 1 and 2, and Week 14 for Cohort 3). Cohort 4 will start the extension phase on Week 12 or have the option of direct entry into the phase 3 study.

This dose/dose regimen may be modified after the final doses for the Phase 3 study have been selected and based on the body weight at the time of possible dose change for Cohorts 1-3 and will not be modified for Cohort 4 as these patients will remain on their initial regimen given the planned study end date of December 2018. Alirocumab administration will be continued until at least 10 weeks before the initiation of the pediatric phase 3 study in the site where the patient is potentially participating or December 2018, whichever comes first.

- During the OLETP:
- A window of \pm 7 days or \pm 14 days according the visit is authorized for each visit planned every 12 weeks from Week 16 or Week 14 to Week 130 for all cohorts (see [Section 1.4](#)),
 - An IVRS/IWRS contact for open-label extension treatment allocation should be done every 2 weeks by the investigator to prepare for using vials in Cohorts 1 & 2 until availability of PFS.

10.1.4.1 Visit 8/Week 16 for Cohorts 1 & 2 or Visit 8/Week 14 for Cohort 3 /Week 12 for Cohort 4 (same visit as the last visit of the main treatment period)

At this visit, patients will undergo end of follow-up period assessments and baseline open-label extension treatment period assessments, as appropriate, concurrently. Study site personnel should review treatment requirements of the open-label extension treatment period with patients and remind patients that dosing in the open-label extension treatment period begins at this visit. The following information will be collected:

- Assess Exclusion Criteria for open-label extension treatment period (see [Section 7.3](#)).

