2.1.3.1 Primary efficacy endpoint(s)

The primary efficacy endpoint is the percent change in calculated LDL-C from baseline to Week 8 in the mITT population, using all calculated LDL-C values during the OLDFI efficacy treatment period defined in [Section 2.3.1](#) (on-treatment estimand). Primary endpoint is defined as: $100 \times (\text{calculated LDL-C value at Week 8} - \text{calculated LDL-C value at baseline}) / \text{calculated LDL-C value at baseline}$.

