2.1.3.2 Secondary efficacy endpoint(s)

The secondary efficacy endpoints are:

- The absolute change in calculated LDL-C from baseline to Week 8 (on-treatment estimand);
- The percent change in LDL-C from baseline to Week 12 only for Cohort 4 (on-treatment estimand);
- The percent change in Apo B, non-HDL-C, Total-C, Lp(a), HDL-C, TG, and Apo A-1 from baseline to Week 8 (on-treatment estimand);
- The proportion of patients reaching calculated LDL-C <130 mg/dL (3.37 mmol/L) at Week 8 (on-treatment estimand);

- The proportion of patients achieving calculated LDL-C level <110 mg/dL (2.84 mmol/L) at Week 8 (on-treatment estimand);
- The absolute change in Apo B, non-HDL-C, Total-C, Lp(a), HDL-C, TG, Apo A-1, and ratio Apo B/Apo A-1 from baseline to Week 8 (on-treatment estimand).

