2.3.1 Efficacy populations

The primary efficacy analysis population for OLDFI period and for the OLDFI/OLE combined period will be the mITT population.

2.3.1.1 *Modified intent-to-treat population*

The modified ITT (mITT) population includes all included patients who received at least one dose or partial dose of IMP injection and had an evaluable primary endpoint during the OLDFI efficacy treatment period. The primary endpoint will be considered as evaluable when both following conditions are met:

- Availability of baseline calculated LDL-C value.
- Availability of at least one calculated LDL-C value during the OLDFI efficacy treatment period and within one of the analysis windows up to Week 8 analysis window.

The OLDFI efficacy treatment period is defined as the period from the first IMP injection to last OLDFI IMP injection + 21 days (for Cohorts 1 & 2) or +35 days (for Cohorts 3 & 4). For patients entering in the OLE, the OLDFI efficacy treatment period will be truncated at the day before the first OLE IMP injection in the extension period.

Patients in the mITT population will be analyzed according to the alirocumab dose group allocated by IVRS.

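### Read literally, the SAP's efficacy-period cut drops the Cohort 4 Week 12 LDL-C value of any patient who starts the extension on the sampling day, although the SAP plans to model Week 12

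*SAP*

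**What the plan says.** **The cut.** SAP 2.3.1.1 (mITT population) and SAP 2.4.4.1 (primary analysis) run the dose-finding (OLDFI) efficacy treatment period to 35 days after the last OLDFI injection for Cohorts 3 and 4. Both then shorten it for patients who enter the OLE: "the OLDFI efficacy treatment period will be truncated at the day before the first OLE IMP injection in the extension period". Neither makes an exception for Cohort 4 or for samples drawn before the injection on the same day.

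**The endpoint.** SAP 2.1.3.1 explains the on-treatment estimand as "using all calculated LDL-C values during the OLDFI efficacy treatment period defined in" SAP 2.3.1. SAP 2.1.3.2 gives the same label to the Cohort 4 endpoint: "The percent change in LDL-C from baseline to Week 12 only for Cohort 4 (on-treatment estimand".

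**The visit.** Cohort 4 has no off-treatment follow-up between the two phases. Protocol 1.4.2, footnote a: "The first visit of the OLE period from the extension phase will overlap with the final visit of the 12-week dose-finding treatment period". Protocol 8.1.2, for Cohort 4: "the first injection administration will start at Week 12 at the end of the 12-week open-label dose finding". Protocol 10.1.4.1 places that injection after the fasting blood draw. Not every patient need follow this path: "Cohort 4 will start the extension phase on Week 12 or have the option of direct entry into the phase 3 study" (Protocol 10.1.4).

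**The planned use of Week 12.** SAP 2.4.4.1 sets out a Cohort 4 MMRM at Weeks 4, 8, 10 and 12, with this data rule: "All post-baseline data available during the open-label dose-finding treatment period and within analysis windows for Cohort 4 will be used". SAP 2.4.4.2.4 includes Week 12 in the OLDFI summaries by time point, and SAP 2.5.4 (Table 3) gives it a window of Days 78 to 92.

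**The concern.** The cut falls one day before the sample that the Week 12 analysis needs. In Cohorts 1 to 3 the weeks off treatment before the extension make the cut harmless. Cohort 4 goes straight from the Week 12 draw to the first OLE injection, so the same wording removes a trough value taken before any OLE drug was given.

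Week 12 is not incidental. Protocol section 4 extended Cohort 4 to 12 weeks so that the higher Q4W doses could be read at steady state after three injections. SAP section 3 makes the OLDFI analysis the primary one for the secondary endpoints and links it to Phase 3 dose selection. If the cut is programmed as written, the Week 12 estimate rests on patients who did not start the OLE that day: those who declined it, went directly to Phase 3, or were injected later. That is a selected subset and could be empty. Two programmers working from different paragraphs of the SAP could also build different Week 12 datasets.

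**Working it through.** **Inputs**
- Day 1 is the first OLDFI injection (SAP 2.5.4), so study day = 7 × week + 1.
- Cohort 4 injections are at Weeks 0, 4 and 8 (SAP 1.4, notes to Figure 2).
- Efficacy period end = the earlier of (last OLDFI injection + 35) and (first OLE injection day − 1) (SAP 2.3.1.1, 2.4.4.1).
- Visit windows are ±3 days at Week 8 and ±7 days at Week 12 (Protocol 1.3.2).
- 10 patients per cohort (SAP 1.3).
- OLE uptake and actual injection dates are not given.

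**1. Reproduce the SAP's figures.** Week 12: 7 × 12 + 1 = Day 85, the target in Table 3. Week 8 dose: 7 × 8 + 1 = Day 57. Then 57 + 35 = Day 92, the upper edge of the Week 12 window. Without the cut, an on-schedule period covers the whole window.

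**2. Apply the cut on schedule.** With the first OLE injection on Day 85, the end is min(92, 85 − 1) = Day 84. The Day 85 sample is inside its analysis window but outside the efficacy period.

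**3. Allow for visit windows.** If sample and injection share day d, the period ends no later than d − 1, so the sample is always out. There are 7 permitted Week 8 days (54 to 60) and 15 permitted Week 12 days (78 to 92), giving 7 × 15 = 105 combinations:

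| Rule | Week 12 sample kept |
|---|---|
| SAP as written, same-day injection | 0 of 105 |
| No cut (+35 days only) | 99 of 105 |
| Cut at the time of the injection | 99 of 105 |

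The 6 losses under the last two rules come from the 35-day limit. A Week 8 dose on Day 54 ends the period on Day 89 and loses Days 90 to 92 (3). Day 55 ends on Day 90 and loses Days 91 and 92 (2). Day 56 ends on Day 91 and loses Day 92 (1).

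**4. Injection on a later day.** If the OLE injection comes at least one day after a Day 85 sample, the cut falls on Day 85 or later and the sample is kept.

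**5. Count.** With k of 10 patients dosed on the sampling day, 10 − k scheduled Week 12 values remain, for k from 0 to 10. At k = 10 there are none. The model's dose-by-time and baseline-by-time terms give Week 12 its own coefficients, so Weeks 4, 8 and 10 cannot supply them.

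**6. What is untouched.**

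| | Last OLDFI dose | Limit without cut | First OLE dose | Period end |
|---|---|---|---|---|
| Cohorts 1 and 2 | Day 43 | 43 + 21 = Day 64 | Day 113 | Day 64 |
| Cohort 3 | Day 29 | 29 + 35 = Day 64 | Day 99 | Day 64 |
| Cohort 4 | Day 57 | 57 + 35 = Day 92 | Day 85 | Day 84 |

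The cut shortens the period only in Cohort 4. Even with the earliest permitted Week 12 visit (85 − 7 = Day 78), it falls on Day 77, after Cohort 4's Week 8 window closes on Day 63. The Week 8 endpoint and mITT membership, which looks only up to the Week 8 window, do not change.

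**The case against.** The strongest reply is that the Week 12 model has its own data rule. That rule refers to the open-label dose-finding treatment period and leaves out the word efficacy. SAP 1.1 makes that period 12 weeks long for Cohort 4, and SAP 1.4 names Week 12 as its end. SAP 2.4.4.1 also attaches Weeks 4 and 8 to the efficacy period when describing the primary model. On this view the specific rule admits the sample and the cut concerns only Week 8.

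This reply has force. A reader might infer that the SAP plainly excludes Week 12, and the documents do not go that far. But the reply does not settle the matter. The Week 12 endpoint carries the on-treatment label, and SAP 2.1.3.1 defines that label by the cut period. SAP 2.1.4 applies the same day-before cut to its OLDFI treatment period, although that is a safety definition. The sections conflict, and the intention to use Week 12 is clear.

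It can also be said that little is at risk. All efficacy analyses are descriptive (SAP 2.4.4), the samples are still drawn, and the combined OLDFI/OLE efficacy period is not cut at the OLE start, so observed Week 12 values would still be shown. That is correct and limits the severity. However, the combined summaries carry no LS means or confidence intervals (SAP 2.4.4.2.4), and SAP section 3 calls those efficacy analyses exploratory.

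**Conclusion.** The point holds as a conflict between SAP sections that, read literally, removes data the plan means to use. Its size is 0 to 10 Week 12 values, assuming 10 Cohort 4 patients and scheduled visits. The documents do not allow a narrower figure. It should be fixed, but it does not threaten the primary analysis.

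Three further inferences are not supported:
- **A late Week 10 sample would stand in for Week 12.** A ±7-day window around the SAP's Day 71 target reaches Day 78, the first day of the Week 12 window. Protocol 10.1.2.6 sets the visit at Day 70 ±7, which ends on Day 77. The overlap depends on which day count is used.
- **The model fails at some particular partial loss.** Whether a point estimate exists does not settle whether the planned SEs and confidence intervals can be obtained, and precision cannot be worked out from the documents. Only the loss of all 10 values is clear.
- **Everyone not dosed on the sampling day keeps the value.** The value must also fall within 35 days of the last OLDFI injection.

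**What to change.** 1. In SAP 2.3.1.1 and 2.4.4.1, end the OLDFI efficacy treatment period at the date and time of the first OLE IMP injection, so that pre-dose samples on that day count.
2. Add a rule for missing times: treat the scheduled Visit 8 sample as pre-dose. This follows the baseline rule in SAP 2.5.3, which accepts values from the day of first administration when a time is missing.
3. State in the Cohort 4 Week 12 paragraph of SAP 2.4.4.1 that this period governs the model.
4. Leave the safety and adverse-event cut-offs in SAP 2.1.4 as they are.

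The SAP already uses this kind of boundary. Baseline runs to the date and time of the first injection (SAP 2.1.3), and the PK population runs to the first OLE injection (SAP 2.3.4). The protocol's own efficacy period (11.4.2.1) has no OLE cut. The cost is short wording edits, one missing-time rule and the matching derivation code, with no new data. The change restores every value that the cut removes, but not those lost to the 35-day limit.

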2.4.4.2 Analyses of secondary efficacy endpoints

2.4.4.2.1 Continuous endpoints anticipated to have a normal distribution

Continuous secondary variables defined in [Section 2.1.3.2](#) anticipated to have a normal distribution (ie, lipids other than TG and Lp(a)) will be analyzed in the mITT population using the same MMRM model as for the primary endpoint with fixed categorical effects of alirocumab doses/dose regimen, planned post-baseline time point up to Week 8, dose-by-time point interaction, as well as, the continuous fixed covariates of corresponding baseline value and baseline value-by-time point interaction.

2.4.4.2.2 Continuous endpoints anticipated to have a non-normal distribution

Continuous secondary efficacy variables defined in [Section 2.1.3.2](#) anticipated to have a non-normal distribution (ie, TG and Lp(a)) will be analyzed in the mITT population using multiple imputation approach for handling of missing values. The percent change from baseline at time point of interest will be derived from observed and imputed lipid values at this time point. Multiple imputation will be followed by robust regression model (4) with endpoint of interest as response variable using M-estimation (using SAS ROBUSTREG procedure) with alirocumab doses/dose regimen, and corresponding baseline value(s) as effects. Means and SEs by dose and by cohort will be retrieved from this model using appropriate contrasts. Combined means estimates for all alirocumab dose groups and for each cohort, with their corresponding SEs, 95% CIs will be provided through the SAS MIANALYZE procedure.

Multiple imputation model

Since in general the missing pattern is anticipated to be not monotone, a two-step approach will be used:

- Step 1: The MCMC method will be used in conjunction with the IMPUTE=MONOTONE option to create an imputed data set with a monotone missing pattern;
- Step 2: Using the monotone data set from step 1, missing data will be imputed using the regression method.

The imputation model for step 1 will include the values of the analyzed parameter at baseline and time-points up to Week 8.

The imputation model for step 2 will include the same variables as in step 1 as well as the dose group.

Data will be log-transformed before imputation process and then back-transformed to create the imputed data sets using the TRANSFORM statement of SAS MI procedure.

2.4.4.2.3 *Binary endpoints*

Binary secondary efficacy endpoints defined in [Section 2.1.3.2](#) will be analyzed using multiple imputation approach for handling of missing values as described for non-normally distributed endpoints but without log-transformation (see [Section 2.4.4.2.2](#) for details about multiple imputation).

For each simulation leading to negative imputed value, another value will be redrawn using MINIMUM option of MI SAS procedure.

The binary endpoint at time point of interest will be derived from observed and imputed lipid values at this time point. Combined estimates for proportion of patients reaching the target for each alirocumab dose groups and for each cohort will be obtained through the SAS MIANALYZE procedure.

2.4.4.2.4 *Summary of results per time point*

For the open-label dose finding treatment period, central laboratory values (in conventional (US) and international units), percent change from baseline, and/or when appropriate absolute change from baseline (in conventional and international units), for calculated LDL-C, Total-C, HDL-C, fasting TG, and non HDL-C at each time point (including Week 10 and W12 time points for Cohort 4), for Lp(a), Apo-B, Apo-A1 and ratio Apo-B/Apo-A1 (absolute change from baseline) at Week 8 time points will be summarized in the mITT population using:

- For lipids other than TG and Lp(a): LS mean and SE for each alirocumab dose group, obtained from the same MMRM models as used for endpoints above and including planned time points (see [Section 2.4.4.2.1](#)) and with raw values, changes from baseline, or percent change from baseline as response variable in the model as appropriate.
- For TG and Lp(a): mean and SE for each alirocumab dose group obtained from multiple imputation approach followed by the robust regression models as used for endpoints above and including planned time points (see [Section 2.4.4.2.2](#)) and with raw values or percent changes from baseline as response variable in the model as appropriate.

In addition, quantitative descriptive summaries by time point (value at visit and % change from baseline) will be presented for all lipids using observed (ie, non-missing) data.

The time profile in %change from baseline of each parameter (except ratio ApoB/Apo A-1 where absolute change will be used) will be plotted according to alirocumab dose received by using LS mean and SE except for TGs and Lp(a). For these 2 parameters, the combined estimate for mean and SE will be used.

For OLDFI /OLE combined period, only quantitative descriptive summaries by time point during the OLDFI/OLE combined efficacy treatment period will be presented for all lipids using observed data in the mITT population. Lipid results pre- versus post-switch to the selected Phase 3 doses will be analyzed separately for Cohorts 1 to 3.

The OLDFI/OLE combined efficacy treatment period is defined as the period from the first IMP injection to last OLE IMP injection + 21 days (for Cohorts 1 & 2) or +35 days (for Cohorts 3 & 4).

